5.3.1 Multiplicity Strategy

To ensure overall control of the type I error rate, following the rejection of the primary efficacy null hypothesis (if the lower limit of the 95% CI [equivalent to the 1-sided 97.5% CI] for the difference of the primary efficacy endpoint is above -1.0 second), the secondary hypotheses will be tested using the Hochberg testing procedure.

For the secondary efficacy endpoints, let:

- H_{0i} refers to the corresponding null hypotheses
- p_i refers to the p-values for H_{0i} , which will be calculated without any multiplicity adjustment where $i = 1, \dots, k$ such that $[1], \dots, [k]$ refer to the order from $p_{[1]} \leq \dots \leq p_{[k]}$.
- Hochberg’s step-up method will proceed as follows:
 - Step 1: If $p_{[k]} < \alpha$ (where α is 0.025, 1-sided), reject all H_{0i} (where $i = 1, \dots, k$), and stop; otherwise go to Step 2.
 - Step 2: If $p_{[k-1]} < \alpha/2$ (where α is 0.025, 1-sided), reject $H_{0[i]}$, $i = 1, \dots, k - 1$, and stop; otherwise go to Step 3.

- ...
- Step k: If $p_{[i]} < \alpha/k$ (where α is 0.025, 1-sided), reject $H_{0[i]}$, $i = 1$, and stop.

Both the adjusted and unadjusted p-values for the secondary efficacy endpoints will be presented.

5.3.2 Subgroup Analyses and Effect of Baseline Factors

Subgroup analyses of the primary endpoint will be conducted to assess the consistency of study treatment effect across various subgroups in the analysis eye. The consistency of the study treatment effect on the primary endpoint will be assessed by replicating the primary efficacy analysis model for each category of the subgroup factor. The study treatment effects and nominal 95% CIs in the analysis eye by category of the following subgroups will be reported in tabular format:

- age category (<65, ≥65 years)
- region (Asia, United Kingdom, United States)
- sex (Male, Female)

In the event of sparsely populated subgroup categories, homogeneous categories may be pooled. The analysis set for the subgroup analyses of the primary endpoint will be the PPS.

5.3.3 Interim Analysis for Efficacy

Not applicable.

6 Safety Analysis Strategy

6.1 Safety Endpoints

The safety endpoints are:

- Extent of exposure
- AEs
- Best Corrected Visual acuity (BCVA)
- Biomicroscopy Findings/ Slit Lamp Examinations (cornea, lens, iris and anterior chamber)

- Quality Complaints

6.2 Safety Hypotheses

There are no formal safety hypotheses in this study. The focus of the safety analysis will be a comprehensive descriptive assessment of safety endpoints listed in Section 6.1.

6.3 Statistical Methods for Safety Analyses

Except otherwise stated, the analysis set for all safety analyses is the Safety Analysis Set as defined in Section 3. Baseline is defined in Section 2.3.

6.3.1 Extent of Exposure

Extent of exposure to study treatment is calculated as duration of exposure to study treatment. Duration of exposure to study treatment is defined as the last day of exposure to study treatment minus the first day of exposure to study treatment, plus 1. In the event that the last day of exposure is unknown, the date of last contact with subject will be used instead. Extent of exposure will be summarized as a continuous measure (N, mean, median, SD, minimum and maximum) and by counts and percentages of subjects in the following categories by study treatment: 1-11 days, 12-38 days, >38 days.

Extent of exposure will be presented overall and by demographic subgroups of interest (refer to Section 5.3.2 for details). The reporting level will be by subject (not eye).

6.3.2 Adverse Events

The applicable definition of an AE is in the study protocol. All AEs occurring from when a subject signs the ICF to when a subject exits the study will be accounted for in the reporting. Analysis and presentation of AEs occurring during the 2 week saline run-in period (the screening period) will be separated from those occurring during the investigational period where a comparative evaluation (descriptive only) of treatment-emergent AEs (TEAEs) is intended. A TEAE is an event not present prior to exposure to investigational product (SYSTANE BALANCE, REFRESH OPTIVE Advanced/ OPTIVE PLUS [UK]) or any pre-existing event that worsens following exposure to investigational product. The period for TEAE analysis starts from exposure to the investigational product to 1 day following cessation of investigational product (it is not expected for the side effects of the investigational product to last more than 24 hours).

Descriptive summaries (subject counts and percentages, event counts) by study treatment for specific AEs will be presented by primary SOC and PT. The SOCs will be presented in

alphabetical order. PTs will be ordered for each study treatment in decreasing proportion in the SYSTANE BALANCE treatment group of interest (study treatment group 1). In addition to an overall presentation of all AEs, reports will be generated for special classes of AEs such as most frequent AEs, ocular AEs, non-ocular AEs, treatment-related AEs, serious AEs (SAEs), AEs by maximum severity (mild, moderate, severe), and AEs resulting in study treatment discontinuation. The overall presentation of all AEs will also be presented by demographic subgroups of interest (refer to Section 5.3.2 for details).

Both subject and event counts will be presented for AEs. Subject counts refer to the number of subjects with the respective AE of interest. Subjects who experience multiple AEs for a PT will be counted once, similarly for subjects with multiple AEs per SOC, for subject counts. Event counts refer to the number of occurrences of the respective AE of interest, regardless of whether a subject already had this event. However for ocular AEs, if an AE was classified as occurring in both eyes, dependent on the event and at the discretion of the medical team the event may only be counted once.

For the legal requirements of ClinicalTrials.gov and EudraCT, two required tables on TEAEs which are not SAEs with an incidence greater than 1% and on treatment emergent SAEs and SAE suspected to be related to study treatment will be provided by SOC and PT.

If for a same patient, several consecutive AEs (irrespective of study treatment causality, seriousness and severity) occurred with the same SOC and PT:

- a single occurrence will be counted if there is ≤ 1 day gap between the end date of the preceding AE and the start date of the consecutive AE
- more than one occurrence will be counted if there is > 1 day gap between the end date of the preceding AE and the start date of the consecutive AE

For occurrence, the presence of at least one SAE / SAE suspected to be related to study treatment / non SAE has to be checked in a block e.g., among AE's in a ≤ 1 day gap block, if at least one SAE is occurring, then one occurrence is calculated for that SAE.

The number of deaths resulting from SAEs suspected to be related to study treatment and SAEs irrespective of study treatment relationship will be provided by SOC and PT.

These reports will be supported by individual subject's listings, as necessary.

Individual subject's listings will be provided for the Screened Set. This listing will contain: AEs that occur after signing the informed consent but prior to exposure to investigational product, TEAEs and post-treatment AEs (if available).

6.3.3 Best Corrected Visual Acuity (BCVA)

Visual acuity assessment will be conducted at the following visits: Day -14 to -7 (Screening), Day 0 (Visit 1), Day 15 (Visit 2), Day 35 (Visit 3) and Early Exit.

The analysis eye will be selected as the eye with the greatest decrease in the number of letters read from baseline to any visit (scheduled or unscheduled). If both eyes have the same level of decrease, the right eye will be selected. Analysis of BCVA will use the data from the analysis eye.

Observed values and change from baseline values for the analysis eye will be presented descriptively (N, mean, median, SD, SE, minimum, and maximum) at each study visit for each study treatment. A plot of mean change in BCVA by study visit and by study treatment with error bars representing ± 1 SE will be presented using the analysis eye. The x-axis will be study visit and the y-axis will be the change in BCVA from baseline.

Counts and percentages of subjects who experience pre-specified category of worst change from baseline across all post-baseline assessments and category of change from baseline to last on-treatment BCVA assessment will be presented according to the following categories: ≤ 4 letter decrease or improvement, 5-9 letter decrease, 10-14 letter decrease, ≥ 15 letter decrease. For change to any visit, a subject will be counted only in the category that represents their worst change from baseline across all post-baseline assessments.

A listing will be provided which presents all subjects with a ≥ 10 letter decrease in BCVA from baseline to any visit. The listing will include the following variables: treatment, investigator, subject, age, sex, race, ethnicity, visit, eye, baseline value, value at the visit and a change from baseline value.

All analyses will also be performed by age and by sex.

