2.1 General definitions

All analyses will be based on assessments according to the investigator, with the exception of the subject reported outcomes (VAS, [REDACTED] questionnaire). This study will consist of the following epochs:

- a screening period
- a study treatment period

Study treatment refers to:

- SYSTANE BALANCE
- REFRESH OPTIVE Advanced/ OPTIVE PLUS (UK)

For efficacy analyses, the study eye will be the worst eye at baseline for each parameter. If the baseline values are equivalent, the right eye will be selected. For safety analyses, the study eye will be selected as the eye with the worst change from baseline to any visit (scheduled or unscheduled). If both eyes have the same level of worsening, the right eye will be selected. A subject may have a different study eye for each parameter of interest, henceforth this eye will be referred to as the analysis eye.

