4.2 Background and demographic characteristics

Demographics, baseline characteristics and key efficacy variables at baseline will be summarized for the RS, FAS, PPS and Safety Analysis Set by study treatment and overall. These tables will also be repeated for the RS for the following subgroups: age, sex and region (see Section 5.3.2 for details on the subgroup categories).

The number and percentage of subjects will be presented for the following categorical variables:

- age (years) (<65, ≥65)
- sex (Female, Male, Unknown, Undifferentiated)

- ethnicity (Hispanic or Latino, not Hispanic or Latino, Not Reported, Unknown)
- race (American Indian or Alaska Native, Asian, Black or African American, Native Hawaiian or Other Pacific Islander, White, Other)
- region (Asia, United Kingdom, United States)
- baseline TFBUT (seconds) (<2, 2-4, >4) (for analysis eye only)
- baseline slit-lamp examination parameters (for analysis eye only)
 - Aqueous flare (None, Faint, Moderate, Marked, Intense)
 - Aqueous cells (< 1, 1-5, 6-15, 16-25, 26-50, >50)
 - Lens (Phakic, Pseudophakic, Aphakic)
 - Status of Lens (No Opacity, Any Opacity, Worsening of Opacity, Not Evaluable)
- baseline horizontal length (Grade 0, Grade 1, Grade 2, Grade 3) (for analysis eye only)
- baseline sagittal height (Grade 0, Grade 1, Grade 2, Grade 3) (for analysis eye only)
- [REDACTED]

Descriptive statistics will be presented for the following continuous variables:

- age (years)
- baseline TFBUT (seconds) (for analysis eye only)
- baseline Global Ocular Discomfort VAS score
- [REDACTED]
- [REDACTED]
- baseline BCVA (for analysis eye only)

All demographic and baseline data will be listed by treatment, center, subject and eye (where applicable) for the RS.

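### BCVA is summarised in the eye chosen for its largest letter loss, so each arm's visit means drift below zero by chance and the baseline rows rest on follow-up data

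*SAP*

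**What the plan says.** SAP 2.1 sets two rules. The efficacy eye is the worse eye at baseline for each parameter. For safety, "the study eye will be selected as the eye with the worst change from baseline to any visit (scheduled or unscheduled"), with ties going to the right eye.

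SAP 6.3.3 applies the safety rule to BCVA: "The analysis eye will be selected as the eye with the greatest decrease in the number of letters read from baseline to any visit". It adds "If both eyes have the same level of decrease, the right eye will be selected" and "Analysis of BCVA will use the data from the analysis eye". The outputs drawn from that eye are:

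- visit-wise summaries by arm, including mean, SD and SE: "Observed values and change from baseline values for the analysis eye will be presented descriptively";
- the figure: "A plot of mean change in BCVA by study visit and by study treatment with error bars representing" one SE either side;
- categories of worst change, and categories of change to the last on-treatment assessment;
- repeats of all of these by age and by sex.

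Section 6.3.3 plans no summary by right and left eye. Besides the selected eye it has only a listing of losses of 10 letters or more, and SAP section 2 provides general listings by subject and eye.

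SAP 6.3.4 picks the slit-lamp eye in the same way, by greatest increase in grade. SAP 4.2 then lists "baseline BCVA (for analysis eye only") and the slit-lamp parameters, also for the analysis eye, among the baseline characteristics for the RS, FAS, PPS and Safety Analysis Set.

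**The concern.** Taking the eye with the worst change suits a table that counts worst changes. It does not suit a mean of change. If two eyes each vary around zero, always keeping the one that fell further gives a negative average. The same applies to the last-assessment categories, which describe one time point but use an eye chosen over all of them.

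The baseline rows have a related fault. A baseline characteristic should be fixed before treatment, but here the eye is identified from later visits. Selection also favours eyes whose baseline reading was high by chance, so the baseline mean rises. A randomized subject with no post-baseline assessment has no change on which to choose, and the tie rule covers equal decreases, not absent ones.

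At stake is how a reader interprets each arm's BCVA change and its error bars. The trial's hypotheses are not at stake.

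**Working it through.** **Inputs from the documents.** Two scheduled post-baseline BCVA visits, Day 15 and Day 35 (SAP 6.3.3). Ties go to the right eye (SAP 6.3.3). 200 evaluable subjects at 1:1, so 100 per arm (SAP section 9).

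**The plan's own figure.** There is none for BCVA. The only sample-size figure is the 200 for TFBUT, used here just for the number per arm. The normal approximation with SD 2.5, margin 1.0, 80% power and one-sided 0.025 gives 2 × (1.960 + 0.842)² × 2.5² / 1.0² = 98.1, so 99 per arm. The noncentral t calculation gives 100 per arm, 200 in total, as stated.

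**Assumptions not in the documents.** True change is zero in both eyes. The SD of one eye's change is 3 to 5 letters. The between-eye correlation of change, ρ, is 0.3 to 0.7, with 0.95 as an extreme. The correlation between the two visits' changes is 0.5, which follows from a shared baseline and equal measurement error. Scores are whole letters. Unscheduled visits are left out.

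**Step 1, one post-baseline visit.** The mean of the lower of two correlated normal changes is -SD × √((1 - ρ)/π). At SD 5 and ρ 0.5 this is -5 × √(0.5/3.1416) = -1.99. Simulation without rounding gives -1.99.

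**Step 2, two visits under the SAP rule.** For each subject, take each eye's lowest change over the two visits, select the eye with the lower value, and average that eye at each visit (400,000 simulated subjects per row). SE is for 100 per arm.

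| SD | ρ | Mean at each visit | SE | Mean / SE |
|---|---|---|---|---|
| 3 | 0.7 | -0.7 | 0.30 | -2.5 |
| 4 | 0.5 | -1.3 | 0.39 | -3.2 |
| 5 | 0.7 | -1.2 | 0.50 | -2.4 |
| 5 | 0.5 | -1.6 | 0.49 | -3.2 |
| 5 | 0.3 | -1.9 | 0.48 | -4.0 |
| 5 | 0.95 | -0.5 | 0.50 | -1.0 |

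An eye fixed without post-baseline data gives 0.0 in every case. The ratio to the SE depends mainly on ρ and hardly on SD. The shift disappears only if both eyes change identically. Over a wider range (SD 3 to 7, ρ 0 to 0.95) it runs from -0.3 to -3.2 letters.

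**Step 3, last-assessment categories.** At SD 5 and ρ 0.5, 27.9% of selected eyes show a loss of 5 or more letters at the second visit, against 18.5% of fixed eyes.

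**Step 4, baseline.** In the same case the selected eye's baseline mean is about 1.05 letters higher than that of a fixed eye.

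**Step 5, between arms.** With equal noise (SD 5, ρ 0.5 in both arms) the simulated difference is within 0.02 letter of zero. With unequal noise, say SD 4 against 6 at ρ 0.5, a difference of about 0.65 letter appears. The documents give no reason to expect unequal noise.

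**Step 6, a real gain.** A true gain of 2 letters at SD 5 and ρ 0.5 would appear as about 0.4, so the rule can also hide improvement.

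**The case against.** The case for leaving the plan alone is a fair one. Worst-eye reporting is prespecified, openly stated and errs toward showing harm. BCVA is shown for both arms side by side, and both receive active products, so a raw change within an arm could not be attributed to a product whichever eye was used. The useful reading is arm against arm, where the expected distortion is zero under equal noise. The smallest BCVA category in SAP 6.3.3 already groups losses of up to 4 letters with improvement, so a shift of 1 or 2 letters is small on the plan's own scale. By-eye listings mean that nothing is lost.

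Most of this stands, and it rules out several stronger readings. A reader might infer that the rule favours one product. The documents do not support that: the rule is the same in both arms and safety is descriptive only. A reader might infer that the trial would conclude that both products reduce vision. The plan draws no such conclusion, and the ratios to the SE above describe how the plot would look; they are not a test. Nor do the documents rank BCVA means above the other safety endpoints in SAP 6.1.

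On the baseline rows, SAP 4.2 does not say which analysis eye it means. The safety rule is the natural reading for BCVA and slit-lamp, but it is an inference.

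What the objection does not answer is that SAP 6.3.3 plans within-arm means and error bars as outputs in their own right, and listings do not correct a biased mean.

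**Conclusion.** The point holds as a presentation fault of low severity. The direction follows from the selection rule whenever true change is zero and the two eyes do not change identically. The size, roughly 1 to 2 letters in the central range and about half a letter when the eyes move almost together, rests wholly on assumed variability and correlations and is not a bound. No decision criterion, hypothesis test or type I error rate is affected. The rule remains reasonable for the worst-change category table, and the listing of losses of 10 letters or more is unaffected.

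The baseline part needs no assumed numbers. On the natural reading of SAP 4.2 with 2.1, 6.3.3 and 6.3.4, the baseline BCVA and slit-lamp rows use an eye chosen from later data, and no eye is defined for randomized subjects without post-baseline assessments.

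**What to change.** In SAP 6.3.3, present visit-wise observed and change values, the SE plot and the last-assessment categories for the right and left eyes separately. Keep the worst-change eye for the worst-change category table, and keep the 10-letter listing as planned. In SAP 4.2, present baseline BCVA and slit-lamp for each eye.

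Do not borrow the TFBUT analysis eye for BCVA. That would choose the eye on an unrelated parameter and drop one dosed eye from the means.

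The cost is SAP wording and a few more table rows and plot lines. No new data are needed, since the protocol has BCVA measured in both eyes at every scheduled visit. SAP 11.1 records that, at Version 3.0, the database was unlocked and the treatment code unbroken, so at that stage the change could be made masked.

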6.3.4 Biomicroscopy Findings/ Slit Lamp Examination

A slit-lamp examination will be performed at the following visits: Day -14 to -7 (Screening), Day 0 (Visit 1), Day 15 (Visit 2), Day 35 (Visit 3) and Early Exit to evaluate the cornea, lens, iris and anterior chamber. Assessments related to the conjunctiva (bulbar, palpebral and limbal conjunctiva), cornea, iris and lids/ lashes will only be entered in the EDC system if clinically significant abnormalities are noted in a subject's medical history or as an AE, if applicable. Ocular signs (aqueous flare, aqueous cells, lens and status of lens) will be captured according to the following grading criteria:

- aqueous flare (None, Faint, Moderate, Marked, Intense)
- aqueous cells (< 1, 1-5, 6-15, 16-25, 26-50, >50)
- lens (Phakic, Pseudophakic, Aphakic)
- status of Lens (No Opacity, Any Opacity, Worsening of Opacity, Not Evaluable)

The analysis eye will be selected as the eye showing the greatest increase in slit-lamp grade from baseline to any visit (scheduled or unscheduled). If both eyes have the same amount of increase, the right eye will be selected. Note that the worst eye will be chosen at the parameter level; therefore it is possible that a given subject may not have the same worst eye for all parameters. Analysis of ocular signs will use the data from the analysis eye.

For each parameter, a shift table showing slit-lamp grade at baseline relative to each post-baseline visit will be presented for the analysis eye by study treatment. For each slit-lamp parameter, counts and percentages of subjects (based on the analysis eye) who experience increase from baseline to any subsequent visit will be presented.

All analyses will also be performed by age and by sex.

A listing will be provided which presents all subjects with an increase in any slit-lamp parameter at any visit compared to the grade of the same eye at baseline. The listing will include all slit-lamp data from all visits with the following variables: treatment, investigator, subject, age, sex, race, ethnicity, visit, eye, parameter, baseline value, and value at the visit.

6.3.5 Quality Complaints

The applicable definition of a device deficiency is in the study protocol. A frequency table showing counts for each Device Deficiency category will be presented.

In addition, a listing of all device deficiencies, as recorded on the Device Deficiency Form will be provided.

6.4 Interim Analysis for Safety

Not applicable.

7 Pharmacokinetic Analysis Strategy

Not applicable.

8 Analysis Strategy for Other Endpoints

Observed lipid layer thickness (LLT) values from all visits will be listed for the RS.

9 Sample Size and Power Calculations

This study will include approximately 220 randomized subjects in a 1:1 ratio of SYSTANE BALANCE to REFRESH OPTIVE Advanced/ OPTIVE PLUS [UK] to achieve 200 evaluable subjects. A total of 200 subjects will provide approximately 80% power to reject the null hypothesis of inferiority of mean change from baseline in TFBUT in the analysis eye at the 0.025 level of significance (1-sided), assuming a study treatment difference of 0.0, a SD of 2.5, and a non-inferiority margin of 1.0 seconds (NQuery, version 7.0).

Table 9-1 Sample size required to achieve 80% and 90% power with different assumed values of SD

Power	Assumed SD	Sample size (total evaluable)
80%	2.5	200
	2.75	240
	3.0	286
90%	2.5	266
	2.75	320
	3.0	382

10 References

Not applicable.

11 Revision History

The reason for the first amended (Version 2.0) Statistical Analysis Plan was to reflect Version 4.0 of the study protocol and Version 1.0 of the UK country specific study protocol and to add clarity to some of the study endpoints.

The reason for the second amended (Version 3.0) Statistical Analysis Plan is to reflect the change to protocol specified analyses (outlined in Section 11.1).

The current version of the Statistical Analysis Plan is based on the following: Version 4.0 of the study protocol and Version 1.0 of the UK country specific study protocol.

